11.12 Replacement of a Subject Who Discontinues Study Treatment

Subjects who receive less than 6 months of study drug will be replaced.

12 CLINICAL MONITORING STRUCTURE

12.1 Safety Monitoring Plan

Study staff will review laboratory and study test results as they become available. Review of test results and communication of findings will be in accordance with OP8 Clinic Operations Standard Operating Procedure for review and assessment of test results. When medically indicated, appropriate follow-up testing and treatment will be offered to participants utilizing the resources and expertise available at the NIH Clinical Center.

13 STATISTICAL CONSIDERATIONS

13.1 Study Hypotheses

Based on the evidence presented above on the impact of statins and ASA on the biomarkers related to inflammation, the coagulation cascade and on cellular markers of activation, we hypothesize that both EC and ART <50 will exhibit reductions in biomarkers and cellular markers of activation and could be grouped for the purposes of the primary end point analysis.

13.2 Sample Size Justification

Those who died in the SMART study had a baseline median sCD14 level of 2.47 µg/mL (IQR 2.19 – 2.91), while matched controls had lower levels at 2.23 µg/mL (IQR 2.01 - 2.63). We powered our study to exhibit a similar effect size.

Assuming a mean of 2.45 µg/mL and a standard deviation of 0.45 µg/mL observed in ART treated subjects in the SMART study (personal communication [name]) and a correlation coefficient of 0.71 (personal communication [name] and [name]), a trial with a total of 40 patients (per treatment arm) has a power of 95% (with type I error of 0.05 based on a one-sample paired difference t test, two-sided) for detecting a 0.20 difference in sCD14 levels between Month 3 and Month 12 visits. This power reduces to

74% when N = 20 and we consider each randomization arm within each group separately (a secondary end point).

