13.5 Efficacy Analysis

The primary endpoint will be set as a change in sCD14 after 9 months of treatment with ASA or ATV, in ECs and in Treated Progressors (ART <50) combined. Assuming 40 patients enroll in each treatment arm, with a mean sCD14 of 2.45 µg/mL and a standard deviation of 0.45 µg/mL, the study has 95% power to detect a reduction of 0.20 in sCD14 levels (See Section 13.2) after 9 months of treatment. The significance of paired differences within each group will be evaluated using two-sided nonparametric (one-sample signed rank) test. As discussed above, this power decreases to 74% when treatment arms are compared individually within each group (as a secondary endpoint, see below). Adjustment for differences in CD4, age and smoking status will be done in any between group (EC vs ART<50) comparisons.

Secondary endpoints, including group comparisons (ASA vs statin and EC vs ART<50) of changes in biomarkers and T cell activation, cardiovascular disease prevalence, and changes in plasma viremia will be evaluated using two-sided nonparametric (Wilcoxon rank-sum) tests. Exploratory analyses comparing paired differences of carotid IMT thickness at Month 0 and Month 12 within each group will be assessed by two-sided nonparametric (one-sample signed rank) tests. Associations between continuous variables (MR measurements and biomarkers and cellular activation markers) will be assessed using Spearman rank order correlation coefficients. Linear regression models will be used to control for factors such as age, smoking, and inflammatory biomarkers. For all evaluations, type I error will be set at 0.05.

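### The 74% power stated for N = 20 is about 70% by the paired t test that Section 13.2 names, and Section 13.5 repeats it in words that can be read as the power for ASA versus ATV

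*Combined protocol and SAP*

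**What the plan says.** Section 13.2 gives all the inputs: "Assuming a mean of 2.45 µg/mL and a standard deviation of 0.45 µg/mL observed in ART treated subjects in the SMART study", "a correlation coefficient of 0.71", and a test specified "with type I error of 0.05 based on a one-sample paired difference t test, two-sided". The power is "for detecting a 0.20 difference in sCD14 levels between Month 3 and Month 12 visits". It is stated as 95% with 40 patients per treatment arm, and then as "74% when N = 20 and we consider each randomization arm within each group separately (a secondary end point".

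Section 13.5 repeats the second figure: "As discussed above, this power decreases to 74% when treatment arms are compared individually within each group (as a secondary endpoint, see below". For the analysis itself it names other tests. On within-group change it says: "The significance of paired differences within each group will be evaluated using two-sided nonparametric (one-sample signed rank) test". The paragraph that follows covers the secondary endpoints, including ASA versus statin, which "will be evaluated using two-sided nonparametric (Wilcoxon rank-sum) tests".

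**The concern.** Both power figures are said to come from one test with one set of inputs, so both should be reproducible. The 95% is; the 74% is not.

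There are four single-arm cells (EC-ASA, EC-ATV, ART-ASA, ART-ATV), and a null result in any of them will be read against the stated power. The chance of missing a true change of 0.20 µg/mL is about 30%, not the implied 26%.

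Section 13.5 adds a second difficulty. Its cross-reference back to Section 13.2 points to the within-arm change, so the phrase about arms being compared may only be loose wording. But its forward reference leads to the paragraph with the rank-sum tests of ASA versus statin, and comparing the two arms in each group is a listed secondary endpoint (Section 3.4.2). A reader could take 74% as the power for that comparison, which it is not.

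**Working it through.** **Inputs (Section 13.2).** SD at one visit 0.45; correlation between visits 0.71; change to detect 0.20; two-sided alpha 0.05; n = 40 (one arm, groups combined) or n = 20 (one arm within one group). I assume equal SDs at Month 3 and Month 12, because the plan gives only one SD.

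**SD of the change.** 0.45 × √(2 × (1 − 0.71)) = 0.45 × √0.58 = 0.3427. Standardised change: 0.20 / 0.3427 = 0.5836.

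**Power of the named test.** Noncentral t with n − 1 degrees of freedom and noncentrality 0.5836 × √n:

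| n | Noncentrality | Critical t | Power, paired t | Power, normal approximation | Plan |
|---|---|---|---|---|---|
| 40 | 3.691 | 2.023 | 94.9% | 95.8% | 95% |
| 20 | 2.610 | 2.093 | 69.7% | 74.2% | 74% |
| 22 | 2.737 | 2.080 | 74.2% | – | – |

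The normal approximation is Φ(noncentrality − 1.96); at n = 20 it is Φ(2.610 − 1.960) = Φ(0.650) = 74.2%. The t test reproduces the primary figure and not the secondary one. By t test, 74% needs 22 per cell, or a change of about 0.21 at n = 20.

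**Could rounded inputs explain it?** With SD 0.445 and correlation 0.715, the t test gives 71.4% at n = 20. Moving the change to 0.205 as well gives 73.5%, but n = 40 then becomes 96.4%, which no longer agrees with the stated 95%.

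**The test planned for the analysis.** Section 13.5 uses the signed-rank test. Simulation (200,000 replicates, exact critical value, same mean and SD of change) gives:

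| Shape of changes (assumed) | n = 20 | n = 40 |
|---|---|---|
| Normal | 67.3% | 94.1% |
| Uniform | 61.4% | 90.8% |
| t with 5 df | 76.0% | 97.3% |
| Laplace | 77.8% | 97.6% |

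**What ASA versus ATV would look like.** The documents give no between-arm difference, so the ones below are assumptions. Two-sample t test on the changes, SD of change 0.343:

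| Assumed difference (µg/mL) | 20 vs 20, within a group | 40 vs 40, groups combined |
|---|---|---|
| 0.10 | 15% | 25% |
| 0.15 | 27% | 49% |
| 0.20 | 44% | 73% |

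The 73% lies close to the stated 74%, but it belongs to the combined groups, and Section 13.5 speaks of comparisons within each group.

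**The case against.** The strongest reply is that 74% is not arbitrary. The normal approximation gives 74.2% and 95.8%; cut to whole percents rather than rounded, these are the printed 74% and 95%. One approximate formula could therefore lie behind both figures. That possibility stands as an account of where the numbers came from: with ordinary rounding neither formula gives both, but the plan does not say how it rounded. It does not rescue the statement, because Section 13.2 labels the calculation a t test, and at n = 20 the two methods differ by more than 4 points.

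On Section 13.5, the cross-reference to Section 13.2 does identify the figure as a within-arm power, and within-arm change in each group is itself a listed secondary endpoint. A careful reader would get there. The forward reference to the rank-sum paragraph still leaves the other reading open.

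It is also fair to say that the signed-rank power can lie above or below 74% depending on the shape of the changes. That is why any signed-rank figure needs its distributional assumption stated. It gives no support to 74% as the power of a t test.

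Finally, the 74% determined no sample size or decision rule, and either value is below 80%. This limits the importance of the error and does not make the number right.

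**Conclusion.** The concern holds. For the test and inputs that Section 13.2 names, power at n = 20 is 69.7% against the stated 74%, an overstatement of about 4 percentage points. This assumes equal SDs at the two visits, full follow-up of 20 per cell, and normally distributed changes. The wording in Section 13.5 is ambiguous rather than plainly wrong, but on one natural reading it attaches 74% to a comparison for which the plan has calculated no power. The primary 95%, the sample size and the analysis methods are unaffected.

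**What to change.** 1. In Sections 13.2 and 13.5, replace 74% with about 70% and keep the paired t test as its basis. If the planned signed-rank test is cited instead, give about 67% and state that this assumes normally distributed changes.
2. In Section 13.5, say that the figure applies when the change within each arm of each group is tested, and that it is not the power for ASA versus ATV.
3. Optionally, add a power for ASA versus ATV. If so, label the between-arm difference as an assumption and show a range, as in the table above.

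The cost is wording only. The stated secondary power becomes slightly less favourable.

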13.3 Safety Analysis

Descriptive statistics with a summary of AEs will be completed at the end of study.

13.4 Planned Interim Analyses

There will be no interim analysis.

13.5 Efficacy Analysis

The primary endpoint will be set as a change in sCD14 after 9 months of treatment with ASA or ATV, in ECs and in Treated Progressors (ART <50) combined. Assuming 40 patients enroll in each treatment arm, with a mean sCD14 of 2.45 µg/mL and a standard deviation of 0.45 µg/mL, the study has 95% power to detect a reduction of 0.20 in sCD14 levels (See Section 13.2) after 9 months of treatment. The significance of paired differences within each group will be evaluated using two-sided nonparametric (one-sample signed rank) test. As discussed above, this power decreases to 74% when treatment arms are compared individually within each group (as a secondary endpoint, see below). Adjustment for differences in CD4, age and smoking status will be done in any between group (EC vs ART<50) comparisons.

Secondary endpoints, including group comparisons (ASA vs statin and EC vs ART<50) of changes in biomarkers and T cell activation, cardiovascular disease prevalence, and changes in plasma viremia will be evaluated using two-sided nonparametric (Wilcoxon rank-sum) tests. Exploratory analyses comparing paired differences of carotid IMT thickness at Month 0 and Month 12 within each group will be assessed by two-sided nonparametric (one-sample signed rank) tests. Associations between continuous variables (MR measurements and biomarkers and cellular activation markers) will be assessed using Spearman rank order correlation coefficients. Linear regression models will be used to control for factors such as age, smoking, and inflammatory biomarkers. For all evaluations, type I error will be set at 0.05.

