In the current 2 group, randomized, open label trial, we intend to study the effects of a lipid lowering agent vs aspirin (ASA) on immune activation in HIV-1 infected participants. One group will consist of ECs who are HIV-1 infected, maintain HIV-RNA levels less than the LLD of commercially available assays in the absence of ART, have no history of ART or opportunistic infections (OIs) and have stable CD4 T cell counts for greater than 3 years. The second group will enroll HIV-1 infected Treated Progressors (henceforth referred to as ART <50) who have maintained HIV-RNA below the limit of detection in commercially available assays (<40, <48, or <50 copies/mL) for greater than 3 years on ART (treatment duration greater than 4 years). Up to 2 months after the screening and enrollment visit, each group will enter a 3 month observation period (to establish baseline values for biomarkers/cellular markers). After 3 months, participants from each group will be randomized to either ASA, 81 mg PO daily, or atorvastatin (ATV), 40 mg (dose adjusted for subjects on antiretroviral regimens with significant interactions, see Section 5.3.1), and will be treated for 9 months, followed by 3 months of a wash out period (see Figure 1). The primary end point will be change of sCD14 after 9 months of study intervention from Month 3 to Month 12 in each treatment arm, with groups combined (EC and ART <50). Secondary objectives will be to compare changes in soluble biomarkers (sCD14, IL-6, D-dimer, hsCRP, sTF, sCD163 and other relevant markers of inflammation and coagulation) and cellular activation markers between study groups and treatment arms (ASA vs statin and EC vs ART<50 and with groups combined), to evaluate cardiovascular (CV) disease prevalence in EC vs ART <50 by MR imaging of carotids, to determine MR measurements and correlations with biomarkers and cellular activation markers, and to investigate changes in plasma viremia as measured by single copy assay over time.

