2.1.7 Targeting Cardiovascular Disease in HIV-infected Persons

A new study proposed by the AIDS Clinical Trial Group (ACTG) is designed to target immune activation in ECs through treatment with ART (A5308, NCT 01777997), with a primary endpoint looking at co-expression of HLA-DR and CD38 on CD8 T cells at 24 and 48 weeks on ART. ART may pose some risks in terms of side effects and may cause a potential decrease or even loss of HIV-specific responses in this unique population. Recently, studies have shown a trend towards decreased mortality with HMG Co-A reductase inhibitors (or statin) therapy [79] and decreased markers of immune activation, as measured by sCD14, with ASA [80] and with statin therapy in HIV positive individuals [81]. In a substudy of the SATURN-HIV trial (a randomized, double-blind trial of ATV in HIV positive individuals, targeting subclinical cardiovascular disease), significant reductions were observed in soluble and cellular markers of monocyte activation after as little as 6 months (24 weeks) on therapy [81], and in a subanalysis of the SMART study, sCD14 was associated with mortality [10]. Additionally, it has been recently reported in a preliminary study that statin use (predominately rosuvastatin and pravastatin) reduces the risk of cancer in HIV-infected persons [82]. We propose to target immune activation with low-dose ASA or ATV therapy in both ECs and ART-treated HIV+ patients with suppressed viremia (ART <50), with change from month 3 in sCD14 as a primary outcome after 9 months of intervention (ASA vs ATV).

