3 STUDY OBJECTIVES

3.1 Primary Objective

- To evaluate changes from baseline in sCD14 after 9 months of treatment with ASA, or ATV, in ECs and in Treated Progressors (ART <50), with the groups combined.

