3.4 Study Endpoints

3.4.1 Primary Endpoint

The primary end point will be change of sCD14 from Month 3 to Month 12 in the 2 groups combined (EC and ART <50).

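### Section 13.5 applies the primary sCD14 test within each group, which by the protocol's own definition pools the two drugs, while the précis and 13.2 define and power it within each treatment arm

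*Combined protocol and SAP*

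**What the plan says.** All references are to the combined protocol and SAP.

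- **Précis (section 1):** the primary endpoint is "change of sCD14 after 9 months of study intervention from Month 3 to Month 12 in each treatment arm, with groups combined". That is one test per drug.
- **Section 13.2:** the power calculation uses 40 patients per treatment arm, "with type I error of 0.05 based on a one-sample paired difference t test, two-sided", for a change of 0.20 µg/mL, and reports 95%.
- **Section 3.1:** "To evaluate changes from baseline in sCD14 after 9 months of treatment with ASA, or ATV, in ECs and in Treated Progressors (ART <50"). It merges the two HIV groups and does not say whether the drugs are analysed separately.
- **Section 3.4.1:** "The primary end point will be change of sCD14 from Month 3 to Month 12 in the 2 groups combined (EC and ART <50"). No arm is named.
- **Section 2.1.7:** "with change from month 3 in sCD14 as a primary outcome after 9 months of intervention (ASA vs ATV").
- **Section 13.5:** the paragraph opens with the two HIV groups combined and 40 patients in each treatment arm. It then gives the test: "The significance of paired differences within each group will be evaluated using two-sided nonparametric (one-sample signed rank) test".
- **Error rate (13.5):** "For all evaluations, type I error will be set at 0.05". No multiplicity rule appears, and nothing says whether one arm or both must show a change.

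Sections 3.2, 3.4.2 and 13.5 list the ASA versus ATV comparison as secondary.

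**The concern.** Section 13.5 is the text an analyst will follow. Throughout the design description, the groups are EC and ART<50, and the arms are ASA and ATV. Section 13.5 keeps to that use in the sentences just after the test: it speaks of treatment arms within each group, and glosses a between-group comparison as EC versus ART<50. An analyst who follows the test sentence literally would therefore run one signed-rank test in the EC patients and one in the ART<50 patients, each mixing both drugs. That contradicts the combined-groups statement at the start of the same paragraph, and it is not the analysis that 13.2 powers.

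Two things are at stake. First, a test that mixes the drugs cannot show that either one lowers sCD14. Second, the trial is open-label and 3.4.1, the formal endpoint definition, does not settle the matter. The set of patients tested could then be chosen after results are known. The number of primary tests and the rule for success are also left open.

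**Working it through.** **Inputs (13.2).** SD 0.45 µg/mL, within-patient correlation 0.71, change 0.20 µg/mL, two-sided alpha 0.05, n = 40 per treatment arm.

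**1. Reproduce the stated power.**
- SD of the change = 0.45 × √(2 × (1 − 0.71)) = 0.3427.
- Standardised change = 0.20 / 0.3427 = 0.584. Noncentrality = 0.584 × √40 = 3.69.
- Paired t test, noncentral t: 94.9%, against 95% stated.
- The signed-rank test of 13.5, simulated with normally distributed changes: about 94%. The change of test from 13.2 to 13.5 costs about one point.

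**2. The literal reading of 13.5 (EC or ART<50, drugs pooled).**
- Each group also has 40 patients. If both drugs lower sCD14 by 0.20, power is again 94.9%.
- Suppose instead that one drug lowers it by 0.20 and the other does nothing. This is an illustration; the documents give no such scenario. Each HIV group has 20 patients on each drug, so its mean change is (0.20 + 0) / 2 = 0.10.
- Simulated power with n = 40 is about 39% for the signed-rank test and about 40% for the paired t test.
- The per-arm test for the effective drug would keep its 94.9%.

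**3. The other two wordings.**
- Section 3.4.1, if read as one pooled test of 80 patients: 0.584 × √80 = 5.22, power 99.9%.
- Section 2.1.7, if read as ASA versus ATV, 40 against 40: standard error = 0.3427 × √(2/40) = 0.0766. The documents give no between-drug difference, so one has to be assumed. At 0.20, power is 73.2% (two-sample t; about 71% for the rank-sum test). At 0.10 it is about 25%. If both drugs lower sCD14 by 0.20, the true difference is zero.

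**4. Error rate for two per-arm tests.**
- The arms contain different patients, so the tests are independent. If neither drug works, the chance of at least one false positive at 0.05 each is 1 − 0.95² = 9.75%.
- Under Holm, the worst case for one arm is a test at 0.025. With n = 40 that gives 90.8% for the paired t test and, by simulation, about 89-90% for the signed-rank test.

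**The case against.** The best case for the plan is that its intent can be recovered. The précis and 13.2 agree on a per-arm analysis, and the primary objective is compatible with it. The lines before the test in 13.5 give 40 patients in each treatment arm and point back to 13.2. The terms are also used loosely: later in 13.5, ASA versus statin is called a group comparison, and section 4.3 heads the two populations as arms. The literal reading is therefore not the only one. This stands, and it limits the point to a correction of wording. It also shows why the correction is needed, since one section uses the same word both ways.

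A reader might infer that the protocol has four rival primary analyses and that the 95% power fails. The documents do not support that. The 95% is right for the per-arm analysis, is matched for the per-group reading if both drugs work, and is exceeded for the pooled one. Only ASA versus ATV falls short. That wording is a parenthesis in the background, it can be read as naming the interventions, and the comparison is listed as secondary in three sections. The 73.2% also needs a 0.20 between-drug difference, whereas 13.2 uses 0.20 as a within-patient change.

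A reader might also infer that the plan carries a 9.75% error rate. That holds only if success in either arm counts as success for the trial, which the plan does not say. In a small Phase 1 biomarker trial that asks a separate question of each of two drugs in separate patients, testing each at 0.05 can be defended.

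**Conclusion.** The point holds as an inconsistency in the operative analysis text. The test sentence in 13.5 names the wrong unit by the protocol's own definitions. It conflicts with its own paragraph, with the précis and with 13.2. Section 3.4.1 does not resolve this because it omits the arm, and 2.1.7 adds a misleading contrast.

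The sample size is not in question: the 95% reproduces at 94.9% for the best-supported analysis. The size of the problem is what happens if 13.5 is followed literally. Neither drug's effect is isolated, and power is about 39% if only one drug works. That figure rests on normally distributed changes, the inputs of 13.2, a 0.20 effect for one drug and none for the other.

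The success rule across the two arms is a real gap. Whether it calls for an adjustment depends on which claim the sponsor intends.

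**What to change.** 1. In the test sentence of 13.5, change the unit to: *within each treatment arm, EC and ART<50 combined*. The same sentence should state n = 40 per arm.
2. Put the same wording in 3.1 (and the matching objective in the Protocol Summary) and in 3.4.1.
3. Reword the parenthesis in 2.1.7 so that it names the two interventions and does not present ASA versus ATV as the primary contrast.
4. Add one sentence on success. Either the two arm tests are separate questions, each at two-sided 0.05 and reported separately, or there is one claim that either arm can satisfy. For the second choice, name an adjustment such as Holm, and revise the power statements in 13.2 and 13.5 to a worst case of about 89-90% per arm for the signed-rank test (90.8% for the paired t test).

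The cost is wording only, with no added patients, visits or assays. Separate questions at 0.05 leave the stated power as it is. Holm lowers the worst-case per-arm power by about four to five points.

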3.2 Secondary Objectives

- Compare changes in soluble biomarkers (sCD14, IL-6, D-dimer, hsCRP, sTF, sCD163 and other relevant markers of inflammation and coagulation) and cellular activation markers between study groups and treatment arms (ASA vs statin and EC vs ART<50 and with groups combined) at 6, 9, 12 months, and after 3 month washout at 15 months. Comparisons between EC and ART<50 will be adjusted for CD4, smoking status and age.
- Evaluate cardiovascular (CV) disease prevalence in EC vs ART <50 by MR imaging of carotids at baseline and follow how it changes over time
- Determine MR measurements and correlations with biomarkers and cellular activation markers
- Investigate changes in plasma viremia as measured by single copy assay
- To assess in an exploratory study the microbiome of EC versus ART<50 groups and the possible influence of ASA or statin therapy
-

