3.4.2 Secondary Endpoints

- To evaluate changes in soluble biomarkers (sCD14, IL-6, D-dimer, hsCRP, sCD163, sTF as well as other relevant markers of inflammation and coagulation) in EC and ART <50 groups treated with ASA or ATV, independently within each group and arm and with groups combined, at 6, 9, and 12 months.
- To evaluate changes in T cell activation (measured by HLA-DR/CD38 co-expression), monocyte immune activation (measured by activated monocyte subsets expressing either CD14⁺⁺CD16⁺ and CD14^{var}CD16⁺ and markers of activation, CCR5 and TF, and migration, CCR2 and CX3CR1), at 6, 9, 12 months of study.
- To investigate differences in HLA type, which has been implicated as a mechanism of viremic control in ECs, between groups and treatment arms, as it relates to treatment response.
- Assess if a wash out period following 9 months of therapy results in biomarker and cellular activation changes after 3 months (Month 15).
- To compare changes of biomarkers and cellular markers between EC and ART <50 groups after adjusting for smoking, CD4 counts and age.
- To compare changes of biomarkers and cellular markers between ATV and ASA arms of each group and in both groups combined.
- To evaluate changes in plasma viral load, as measured by single copy assay in EC and ART <50 groups treated with ASA or ATV at baseline, 3 and 12 months.
- Assess toxicity profile of ASA versus ATV in the study population.
- Assess prevalent atherosclerotic disease in EC vs ART<50 by MR imaging of carotids.
- Assess changes in MR imaging of carotids after 9 months of statin or ASA in each group and both groups combined.
- Correlate MR vascular imaging with soluble and cellular biomarkers of inflammation.

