6.3 Randomization

The NIH Pharmacy Department will carry out blocked, open-label, randomization using a random number generator. At the Month 3 study visit, ECs and Treated Progressors will be separately randomized 1:1 to open label ASA or ATV arms.

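### The secondary ASA-versus-ATV rank-sum test is valid, but it leaves out the Month 3 value as a covariate and, with groups combined, the randomisation stratum; a baseline-adjusted rank analysis would use both.

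*Combined protocol and SAP*

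**What the plan says.** Section 6.3 sets the randomisation: "ECs and Treated Progressors will be separately randomized 1:1 to open label ASA or ATV arms". EC/ART<50 is therefore a randomisation stratum.

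Section 3.4.2 lists two relevant secondary comparisons. The first is between arms: "To compare changes of biomarkers and cellular markers between ATV and ASA arms of each group and in both groups combined". The second is between patient groups: "To compare changes of biomarkers and cellular markers between EC and ART <50 groups after adjusting for smoking, CD4 counts and age".

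Section 13.5 gives one method for both. It covers "Secondary endpoints, including group comparisons (ASA vs statin and EC vs ART<50) of changes in biomarkers and T cell activation", which, with disease prevalence and viremia, "will be evaluated using two-sided nonparametric (Wilcoxon rank-sum) tests". No stratification and no Month 3 covariate are stated.

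On adjustment of EC versus ART<50, section 3.2 states: "Comparisons between EC and ART<50 will be adjusted for CD4, smoking status and age". Section 13.5 repeats the promise: "Adjustment for differences in CD4, age and smoking status will be done in any between group (EC vs ART<50) comparisons". Later in 13.5, after the sentence on Spearman correlations, comes a general statement: "Linear regression models will be used to control for factors such as age, smoking, and inflammatory biomarkers".

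**The concern.** Two pieces of information are available for ASA versus ATV and go unused. The Month 3 value enters only by subtraction, which removes less noise than covariate adjustment when the correlation between visits is well below 1. With EC and ART<50 combined, any difference in how the two groups change is left in as noise, although the design balances arms within each group. At stake is power for a secondary contrast, for which the plan states no effect size and no power.

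For EC versus ART<50, the named test takes no covariates, so it cannot by itself deliver the promised adjustment. The regression sentence could, but it is not tied to this comparison and does not list CD4.

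**Working it through.** **Inputs.** From section 13.2: SD 0.45 µg/mL at one visit, correlation r = 0.71, two-sided alpha 0.05. From the design: 40 per arm, 20 per arm within each group. Assumed, because the documents give no value: a between-arm difference of 0.20, and a difference of 0.30 between the mean changes of EC and ART<50.

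**The plan's own figure.** SD of change = 0.45 × √(2 × (1 − 0.71)) = 0.343. Standardised change = 0.20/0.343 = 0.584. The one-sample two-sided t test with n = 40 has power 94.9%, which reproduces the stated 95%. With n = 20 the t test gives 69.7%; the stated 74% matches the normal approximation (74.2%). Both figures concern within-arm change, not the comparison of arms.

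**Month 3 as covariate.** Residual variance after adjustment, relative to the variance of change, is (1 − r²)/(2(1 − r)) = (1 + r)/2 = 0.855. The residual SD is 0.45 × √(1 − 0.71²) = 0.317. With 40 per arm and a difference of 0.20:
- t test on change: 73.2%
- rank-sum on change (efficiency 0.955 on normal data): 71.2%
- ANCOVA on the raw scale: 79.6%

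Rank ANCOVA was assessed by simulation, regressing the ranked Month 12 value on arm, ranked Month 3 value and stratum. Power with groups combined:

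| Setting (difference 0.20 unless stated) | Rank-sum | Rank ANCOVA | Raw ANCOVA |
|---|---|---|---|
| Normal, r 0.71 | 70-71% | 74-75% | 79% |
| Assumed mild right skew (shifted lognormal, sigma 0.40) | 79-80% | 87% | 79% |
| Normal, difference 0.10 | 24% | 26% | 29% |
| Normal, r 0.6 | 56% | 64% | – |
| Normal, r 0.8 | 85% | 85% | – |
| Normal, r 0.85 | 93% | 93% | – |

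Within one group (20 per arm, normal, 0.20) the three figures are 41%, 44% and 48%. Type I error of rank ANCOVA was 4-5% in the null runs.

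**Stratum.** A difference of 0.30 between the groups' mean changes adds (0.30/2)² = 0.0225 to the variance that the unstratified test sees: 0.1175 + 0.0225 = 0.1400. The sampling variance of the arm contrast stays at the within-stratum 0.1175. The effective critical value becomes 1.96 × √(0.1400/0.1175) = 2.14, a two-sided null rejection rate of about 3.2%. Simulation on normal data agrees: about 3% under the null, and power for 0.20 of about 64% for the unstratified rank-sum, 70% for van Elteren and 74% for rank ANCOVA.

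**EC versus ART<50.** Sections 3.2, 3.4.2 and 13.5 all promise adjustment for CD4, age and smoking. The regression sentence in 13.5 names age and smoking in an open list, omits CD4, and attaches to no outcome or comparison. The pieces are present and the link between them is missing. To show why the adjusted result should decide: with no true adjusted difference, a covariate differing by an assumed 0.5 SD between groups and correlating 0.2 to 0.5 with change makes an unadjusted rank-sum test reject 7-20% of the time, against about 5% for adjusted regression.

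**The case against.** The strongest reply is that a valid test on a secondary endpoint has been chosen, and the gain from changing it is 3 to 5 points on normal data, about 2 points if the arms differ by only 0.10, and nil at r of 0.8 or above. The 0.20 in section 13.2 is a within-patient change, and section 13.1 expects markers to fall under both drugs, so the arms may differ by less. All of that stands, and it is why this is an efficiency point.

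The replacement also has a cost. Rank ANCOVA gives no estimate in µg/mL. A Hodges-Lehmann interval for change reported beside it belongs to the rank-sum test, so the interval and the p value can disagree. That stands too and should be acknowledged in the SAP. Raw-scale ANCOVA avoids the problem and does best on normal data, but under the assumed mild skew it gains nothing over rank-sum.

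Four stronger readings are tempting, and the documents do not support them:
- *The rank-sum test is invalid.* It holds its level and becomes conservative if the groups change differently.
- *Month 3 and the stratum are not used at all.* The test is on change from Month 3, and the within-group comparisons respect the stratum. Only the covariate use, and the stratum in the combined comparison, are missing.
- *The SMART quartiles in 13.2 imply strong skew and hence large gains.* Lognormal shapes set to the quartile asymmetry with SD held at 0.45 have interquartile ranges of 0.45 and 0.35, against 0.72 (2.91 − 2.19) and 0.62 (2.63 − 2.01) in the text. They fit neither group, so no gain can be read from them.
- *EC versus ART<50 will be analysed unadjusted.* Adjustment is promised three times and a regression tool is named, so the 7-20% is not an error rate of the plan.

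**Conclusion.** The point holds as a cheap improvement to secondary analyses, not as an error. For ASA versus ATV, adding Month 3 and stratum on the rank scale lifts power from about 70-71% to 74-75% on normal data, from 79-80% to 87% under an assumed mild skew, and from about 64% to 74% if EC and ART<50 change differently by 0.30. These figures rest on the plan's SD and correlation and on between-arm and between-group differences that are assumptions. They do not promise a gain if the true correlation is 0.8 or higher with normal data. For EC versus ART<50, the matter is one of missing wording.

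**What to change.** **ASA versus ATV.** Pre-specify rank ANCOVA: ranked Month 12 marker on arm and ranked Month 3 value, plus EC/ART<50 stratum for the combined comparison. State whether ranks are pooled or taken within stratum (74% and 73% on normal data, so little depends on it). Keep the rank-sum test as sensitivity, in its van Elteren form when groups are combined. Report the Hodges-Lehmann difference in change with its 95% CI, and say which result governs if the two disagree.

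**EC versus ART<50 (minor).** Add a sentence stating that the promised adjustment is delivered by the regression named in 13.5, with CD4, age, smoking and treatment arm as covariates, and that this adjusted result decides while the unadjusted rank-sum test is descriptive.

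**Cost.** SAP wording only, settled before the data are examined. Sections 6.4 and 6.6 and Appendix B already provide CD4 and research samples at Months 3 and 12. Section 7.1 mentions social history only, so confirm that smoking status is captured as a data field.
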